**Evaluation of Best Overall Response**

The best overall response is the best response recorded from the start of the treatment until disease progression/recurrence (taking as reference for progressive disease the smallest measurements recorded since the treatment started). The patient's best response assignment will depend on the achievement of both measurement and confirmation criteria.

Target Lesions	Non-Target Lesions	New Lesions	Overall Response	Best Response for this Category Also Requires
CR	CR	No	CR	> 4 weeks confirmation
CR	Non-CR/ Non-PD	No	PR	> 4 weeks confirmation
PR	Non-PD	No	PR	
SD	Non-PD	No	SD	documented at least once > 4 weeks from baseline
PD	Any	Yes or No	PD	no prior SD, PR or CR
Any	PD*	Yes or No	PD	
Any	Any	Yes	PD	

---

\* In exceptional circumstances, unequivocal progression in non-target lesions may be accepted as disease progression

## **Duration of Response**

### **Duration of overall response**

The duration of overall response is measured from the time measurement criteria are met for CR or PR (whichever is first recorded) until the first date that recurrent or progressive disease is objectively documented (taking as reference for progressive disease the smallest measurements recorded since the treatment started).

The duration of overall CR is measured from the time measurement criteria are first met for CR until the first date that recurrent disease is objectively documented.

### **Duration of stable disease**

Stable disease is measured from the start of the treatment until the criteria for progression are met, taking as reference the smallest measurements recorded since the treatment started.

### **Progression-Free Survival**

Progression-free survival (PFS) is defined as the duration of time from start of treatment to time of progression.

## **7.4 Evaluation of Safety**

Analyses will be performed for all patients having received at least one dose of study drug. The study will use the [CTCAE v4.0](#) for reporting of non-hematologic adverse events and modified criteria for hematologic adverse events.

For multicenter studies, the Principal Investigator at the UCSF Coordinating Center will hold the role of Study Chair. The Study Chair is responsible for the overall conduct of the study and for monitoring its safety and progress at all participating sites.

## **7.5 Definitions of Adverse Events**

### **7.5.1 Adverse Event**

An adverse event (also known as an adverse experience) is defined as any untoward medical occurrence associated with the use of a drug in humans, whether or not considered drug related. More specifically, an adverse event (can be any unfavorable and unintended sign (e.g., an abnormal laboratory finding), symptom, or disease temporally associated with the use of a drug, without any judgment about causality. An adverse event can arise from any use of the drug (e.g., off-label use, use in combination with another drug) and from any route of administration, formulation, or dose, including an overdose.

### **7.5.2 Adverse reaction**

An adverse reaction is defined as any adverse event caused by the use of a drug. Adverse reactions are a subset of all suspected adverse reactions for which there is reason to conclude that the drug caused the event.

### 7.5.2.1 Suspected

A suspected adverse reaction is defined as any adverse event for which there is a reasonable possibility that the drug caused the adverse event. For the purposes of IND safety reporting, “reasonable possibility” indicates that there is evidence to suggest a causal relationship between the drug and the adverse event. A suspected adverse reaction implies a lesser degree of certainty about causality than an adverse reaction.

### 7.5.2.2 Unexpected

An adverse event or suspected adverse reaction is considered *unexpected* if it is not listed in the investigator brochure or package insert(s), or is not listed at the specificity or severity that has been observed, or, if an investigator brochure is not required or available, is not consistent with the risk information described in the general investigational plan or elsewhere in the current application.

“Unexpected,” as used in this definition, also refers to adverse events or suspected adverse reactions that are mentioned in the investigator brochure as occurring with a class of drugs or as anticipated from the pharmacological properties of the drug, but are not specifically mentioned as occurring with the particular drug under investigation.

Adverse events that would be anticipated to occur as part of the disease process are considered *unexpected* for the purposes of reporting because they would not be listed in the investigator brochure. For example, a certain number of non-acute deaths in a cancer trial would be anticipated as an outcome of the underlying disease, but such deaths would generally not be listed as a suspected adverse reaction in the investigator brochure.

Some adverse events are listed in the Investigator Brochure as occurring with the same class of drugs, or as anticipated from the pharmacological properties of the drug, even though they have not been observed with the drug under investigation. Such events would be considered *unexpected* until they have been observed with the drug under investigation. For example, although angioedema is anticipated to occur in some patients exposed to drugs in the ACE inhibitor class and angioedema would be described in the investigator brochure as a class effect, the first case of angioedema observed with the drug under investigation should be considered *unexpected* for reporting purposes.

### 7.5.2.3 Serious

An adverse event or suspected adverse reaction is considered *serious* if, in the view of either the investigator or sponsor, it results in any of the following outcomes:

- Death
- Life-threatening adverse event
- Inpatient hospitalization or prolongation of existing hospitalization
- A persistent or significant incapacity or substantial disruption of the ability to conduct normal life function
- Congenital anomaly/birth defect

Important medical events that may not result in death, are life-threatening, or require hospitalization may be considered serious when, based upon appropriate medical judgment, they may jeopardize the patient or subject and may require medical or surgical intervention to prevent one of the outcomes listed in this definition. Examples of such

medical events include allergic bronchospasm requiring intensive treatment in an emergency room or at home, blood dyscrasias or convulsions that do not result in inpatient hospitalization, or the development of drug dependency or drug abuse.

#### 7.5.2.4 Life-threatening

An adverse event or suspected adverse reaction is considered *life-threatening* if, in the view of either the investigator or sponsor, its occurrence places the patient or subject at immediate risk of death. It does not include an adverse event or suspected adverse reaction that, had it occurred in a more severe form, might have caused death.

### 7.6 Recording of an Adverse Event

All grade 3 and above adverse events will be entered into OnCore®, whether or not the event is believed to be associated with use of the study drug. Data about these events and their severity will be recorded using the NCI CTCAE v4.0.

The Investigator will assign attribution of the possible association of the event with use of the investigational drug, and this information will be entered into OnCore® using the classification system listed below:

Relationship	Attribution	Description
Unrelated to investigational drug/intervention	Unrelated	The AE is clearly NOT related to the intervention
	Unlikely	The AE is doubtfully related to the intervention
Related to investigational drug/intervention	Possible	The AE may be related to the intervention
	Probable	The AE is likely related to the intervention
	Definite	The AE is clearly related to the intervention

Signs or symptoms reported as adverse events will be graded and recorded by the Investigator according to the CTCAE. When specific adverse events are not listed in the CTCAE they will be graded by the Investigator as *none, mild, moderate* or *severe* according to the following grades and definitions:

Grade 0	No AE (or within normal limits)
Grade 1	Mild; asymptomatic or mild symptoms; clinical or diagnostic observations only; intervention not indicated
Grade 2	Moderate; minimal, local, or noninvasive intervention (e.g., packing, cautery) indicated; limiting age-appropriate instrumental activities of daily living (ADL)
Grade 3:	Severe or medically significant but not immediately life-threatening; hospitalization or prolongation of hospitalization indicated; disabling; limiting self-care ADL
Grade 4:	Life-threatening consequences; urgent intervention indicated
Grade 5:	Death related to AE

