## 7.8 Adverse Events Monitoring

All adverse events, whether or not unexpected, and whether or not considered to be associated with the use of the study drug, will be entered into OnCore®, as noted above.

The Investigator will assess all adverse events and determine reportability requirements to the UCSF Data and Safety Monitoring Committee (DSMC) and UCSF's Institutional Review Board, the Institutional Review Board (IRB); and, when the study is conducted under an Investigational New Drug Application (IND), to the Food and Drug Administration (FDA) if it meets the FDA reporting criteria.

All adverse events entered into OnCore® will be reviewed by the Helen Diller Family Comprehensive Cancer Center Site Committee on a monthly basis. The Site Committee will review and discuss at each monthly meeting the selected toxicity, the toxicity grade, and the attribution of relationship of the adverse event to the administration of the study drug(s).

All grade(s) 3-5 adverse events entered into OnCore® will be reviewed on a monthly basis at the Site Committee meetings. The Site Committee will review and discuss the selected toxicity, the toxicity grade, and the attribution of relationship of the adverse event to the administration of the study drug(s).

In addition, all suspected adverse reactions considered "serious" entered into OnCore®, will be reviewed and monitored by the Data and Safety Monitoring Committee on an ongoing basis and discussed at DSMC meetings, which take place every six weeks.

For a detailed description of the Data and Safety Monitoring Plan, please refer Appendix 2 Multicenter Institutional Studies.

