#### Safety

Safety endpoints include incidence of worst grade adverse events; incidence of deaths and other serious and significant adverse events; and incidence of worst grade laboratory abnormalities. All recorded adverse events will be listed and tabulated by system organ class, preferred term, and by dose group and cohort and coded according to the Medical Dictionary for Regulatory Activities (MedDRA). Vital signs, physical examinations, clinical laboratory test, medical history, ECOG, and ECGs results will be listed and summarized by dose groups.

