### **8.5 Evaluation of Safety**

Analyses will be performed for all patients having received at least one dose of study drug. The study will use the NCI CTCAE v4.0.

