## Adverse Event Review and Monitoring

### Adverse Event Monitoring

All Grade 3-5 Adverse Events, whether or not unexpected, and whether or not considered to be associated with the use of study drug, will be entered into OnCore®, UCSF's Clinical Trial Management System.

All Grade 3-5 adverse events entered into OnCore® will be reviewed on a monthly basis at the UCSF Site Committee meetings. All clinically significant adverse events must be reported to the UCSF Coordinating Center by the participating sites within 10 business days of becoming aware of the event or during the next scheduled quarterly conference call, whichever is sooner. The UCSF Site Committee will review and discuss the selected toxicity, the toxicity grade, and the attribution of relationship of the adverse event to the administration of the study drug(s) from the UCSF Coordinating Center and the participating sites.

In addition, all suspected adverse reactions considered "serious" must be entered in OnCore® and reported to the UCSF Coordinating Center within 1 business day. The suspected adverse reactions considered "serious" will be reviewed and monitored by the Data and Safety Monitoring Committee on an ongoing basis and discussed at the DSMC meeting, which take place every six (6) weeks.

If a death occurs during the treatment phase of the study or within 30 days after the last administration of the study drug(s) and is determined to be related either to the investigational drug or any research related procedure, the Study Chair at the UCSF Coordinating Center or the assigned designee must be notified within 1 business day from the participating site(s) and the Study Chair must then notify the DSMC Chair or qualified alternate within 1 business day of this notification. The contact may be by phone or e-mail.

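### Section 7.6 and Appendix 2 ask for OnCore entry of grade 3 and above adverse events, section 7.8 asks for all grades, and the safety analysis in 8.4.3 needs all grades

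*Combined protocol and SAP*

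**What the plan says.** Three places in the protocol set a rule for entering adverse events in OnCore.

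- Section 7.6: "All grade 3 and above adverse events will be entered into OnCore", whatever their attribution.
- Section 7.8, on the same database: "All adverse events, whether or not unexpected, and whether or not considered to be associated with the use of the study drug, will be entered". The sentence gives no grade limit and closes with a back-reference to the preceding rule ("as noted above").
- Appendix 2, Adverse Event Monitoring, to which 7.8 sends the reader for detail: "All Grade 3-5 Adverse Events, whether or not unexpected". It adds that serious suspected reactions are entered, with no grade limit.

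The scope of the Site Committee's monthly review also varies. Section 7.8 first has all entered events reviewed, then in the next paragraph has grade 3-5 events reviewed. Appendix 2 has grade 3-5 only.

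On the analysis side, section 2.2 makes the safety profile a secondary objective. Section 8.4.3 says "Safety endpoints include incidence of worst grade adverse events", with tables built from recorded events. Section 9.7 puts all study data in OnCore through the case report forms.

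On grading, section 7.4 uses CTCAE v4.0 for non-haematologic events and "modified criteria for hematologic adverse events", which the text does not define. Section 8.5 says without qualification: "The study will use the NCI CTCAE v4.0". Sections 5.3 and 7.6 also use CTCAE v4.0.

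**The concern.** A coordinator who reads 7.6, the section that governs recording, or Appendix 2 would reasonably stop at grade 3. One who reads 7.8 would enter everything. The cross-reference in 7.8 does not settle it, because the rule it points back to is the narrower one.

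The choice matters because a worst-grade table needs each patient's highest grade, including 1 and 2. Under a grade 3 threshold, a patient whose worst nausea was grade 2 looks the same in the database as a patient who had none. For non-serious symptomatic events the grade 1 and 2 rows empty, and any-grade incidence shrinks towards grade 3-5 incidence. Section 1.4 describes the commonest selinexor toxicities as mostly grade 1-2, so those rows hold much of what the safety objective is meant to describe. Table 5.3 also ties dose changes to unresolved grade 2 fatigue, anorexia and nausea, so some unentered events would be ones that altered treatment.

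Section 3.1 plans several centres. If they follow different sections, pooled rates would mix two definitions of what was recorded.

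**Working it through.** The plan states no figure on this point, so the check is a comparison of the text followed by an illustration of size.

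**Step 1. The entry rules side by side.**

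| Place | Events to be entered in OnCore |
|---|---|
| 7.6 | Grade 3 and above, any attribution |
| 7.8 | All, any attribution, with a reference back to the rule above |
| Appendix 2 | Grade 3-5, any attribution; plus serious suspected reactions at any grade |
| Needed by 8.4.3 | All grades |

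Only 7.8 supplies what 8.4.3 needs.

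**Step 2. What a grade 3 threshold would remove.** It would remove grade 1-2 events that are not serious suspected reactions. It would leave:

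- grade 3-5 incidence, since those events are entered under every rule;
- serious suspected reactions, entered at any grade under Appendix 2;
- worst-grade laboratory abnormalities, a separate endpoint in 8.4.3 supported by blood count and chemistry at each cycle (Table 6.1);
- the first safety rule in 8.3, which counts grade 3 or 4 toxicity in the first 10 patients.

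The exposure is therefore non-serious symptomatic grade 1-2 events.

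**Step 3. Illustration of size.** Inputs: N = 54 patients at most (section 3.2), and phase 1 rates p from section 1.4. Let s be the share of affected patients whose worst grade is 1-2. The documents say only that most of these events are grade 1-2, so s is an assumption, shown at 51%, 75% and 95%. It also treats a statement about events as if it held for each patient's worst grade.

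Expected patients with the toxicity = N × p. Expected patients not entered = N × p × s.

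| Toxicity | p | 54 × p | s = 51% | s = 75% | s = 95% |
|---|---|---|---|---|---|
| Fatigue | 0.73 | 39.4 | 20.1 | 29.6 | 37.4 |
| Nausea | 0.70 | 37.8 | 19.3 | 28.3 | 35.9 |
| Anorexia | 0.57 | 30.8 | 15.7 | 23.1 | 29.2 |
| Vomiting | 0.49 | 26.5 | 13.5 | 19.8 | 25.1 |
| Total pairs | 2.49 | 134.5 | 68.6 | 100.8 | 127.7 |

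The proportion not entered is s itself, whatever the rates. The counts scale with the rates and should be read as indicative.

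**The case against.** The best defence is that the three passages can all be obeyed at once. Neither 7.6 nor Appendix 2 says *only*, and neither forbids entry of lower grades. Section 7.8 requires all events, 9.7 sends all study data to OnCore, and 7.6 goes on to define grades 1 and 2 and has the investigator grade and record reported signs and symptoms. A site that satisfied every sentence would enter everything. This stands to the extent that the loss is conditional on how sites read the text. It does not remove the problem: a stated threshold in the recording section, repeated in the monitoring plan, is naturally read as a threshold.

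The phase 1 rates also do not transfer directly. They come from dose escalation in mg/m² at 8 or 10 doses per cycle. This trial gives a 60 mg flat dose six times per cycle with antiemetic prophylaxis, and 1.4 says aggressive prophylaxis can greatly reduce or eliminate these events. That stands, and it is why the counts above are only indicative.

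A reader might infer three stronger claims that the documents do not support.

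- *The worst-grade tables could not be produced.* They could, but with the lower grades understated. Adverse events are assessed at the scheduled visits, so grade 1-2 events may survive in source records; the loss is from the analysis database.
- *The safety stopping rules are compromised.* The grade 3-4 count is untouched by the entry threshold. The other toxicity rule in 8.3 counts toxicity that rules out dosing at every level. It is not defined by grade, and the documents do not show that it depends on entry of grade 1-2 events.
- *The undefined haematologic criteria change the 8.3 count.* Table 5.3 gives numeric neutrophil and platelet cut-offs by grade, three sections name CTCAE v4.0, and no alternative grading is given that would move a patient across the threshold.

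**Conclusion.** The inconsistency is real and stands in the current text. It should be fixed, but it bears on one descriptive secondary endpoint; the primary endpoint and the two-stage decision do not depend on grade 1-2 entry.

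If sites follow 7.6 or Appendix 2, any-grade and worst-grade incidence of non-serious symptomatic events will be understated. If most affected patients have grade 1-2 as their worst grade, more than half of the patient-toxicity pairs for the four commonest toxicities would be absent: roughly 69 to 128 of 134 at phase 1 rates and full enrolment. This rests on three assumptions: that sites read the threshold as a limit, that the phase 1 grade mix carries over to this regimen, and that the grade 1-2 share lies between 51% and 95%. If sites follow 7.8, nothing is lost. If they differ, the pooled rates are not interpretable as a single measure.

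The undefined haematologic criteria in 7.4 are a separate, minor drafting point with no demonstrated numerical effect.

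**What to change.** State in 7.6 and Appendix 2, in line with 7.8, that adverse events of every grade and attribution are entered in OnCore with CTCAE v4.0 grade and attribution. The back-reference in 7.8 then becomes correct, and 8.4.3 has the data it needs.

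Reconcile the two monthly review statements in 7.8 and the one in Appendix 2 into a single scope. One of the statements in 7.8 has all entered events reviewed, so limiting committee review to grade 3-5 would be a reduction in oversight. If that is intended, it should be stated as a decision and not arrive as a by-product of the rewording.

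Separately, define the modified haematologic criteria in 7.4 or delete the phrase. The documents do not show whether a modification was intended, so the sponsor has to say which.

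The cost is a wording amendment and some extra data entry for grade 1-2 events. The design, sample size and visit schedule do not change.

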## 7.7 Follow-up of Adverse Events

All adverse events will be followed with appropriate medical management until resolved. Patients removed from study for unacceptable adverse events will be followed until resolution or stabilization of the adverse event. For selected adverse events for which administration of the investigational drug was stopped, a re-challenge of the subject with the investigational drug may be conducted if considered both safe and ethical by the Investigator.

## 7.8 Adverse Events Monitoring

All adverse events, whether or not unexpected, and whether or not considered to be associated with the use of the study drug, will be entered into OnCore®, as noted above.

The Investigator will assess all adverse events and determine reportability requirements to the UCSF Data and Safety Monitoring Committee (DSMC) and UCSF's Institutional Review Board, the Institutional Review Board (IRB); and, when the study is conducted under an Investigational New Drug Application (IND), to the Food and Drug Administration (FDA) if it meets the FDA reporting criteria.

All adverse events entered into OnCore® will be reviewed by the Helen Diller Family Comprehensive Cancer Center Site Committee on a monthly basis. The Site Committee will review and discuss at each monthly meeting the selected toxicity, the toxicity grade, and the attribution of relationship of the adverse event to the administration of the study drug(s).

All grade(s) 3-5 adverse events entered into OnCore® will be reviewed on a monthly basis at the Site Committee meetings. The Site Committee will review and discuss the selected toxicity, the toxicity grade, and the attribution of relationship of the adverse event to the administration of the study drug(s).

In addition, all suspected adverse reactions considered "serious" entered into OnCore®, will be reviewed and monitored by the Data and Safety Monitoring Committee on an ongoing basis and discussed at DSMC meetings, which take place every six weeks.

For a detailed description of the Data and Safety Monitoring Plan, please refer Appendix 2 Multicenter Institutional Studies.

